### **22.3 Processing Data Collection Forms**

TRTT Clinical Coordinators will collect TRTT data on paper data collection forms and enter this data online at the TRTT website. Data entry screens will have the same fields and prompts that are recorded on the paper data collection forms. Integrity checks are implemented at the database level as data is being entered. The database will highlight missing and questionable (e.g., out-of-range) data entries, including those related to user-defined dictionary look ups, numeric range tests, date, currency and character-specific formatting. Staff at the DCC will also

perform data checks to correct data following receipt of data feedback information from Clinical Centers.

### **22.3.1 Validation of Data Collection Forms**

All data items will be validated against criteria specified in the data dictionary. Validation includes checks for consistency with other responses and completeness. These errors will be flagged during the data entry process and may include coding for cross-edits, across forms edits, and any special edits. The cross-edits can be as simple as comparing one variable with another or they can be more difficult such as checking a calculated score and then making certain decisions based on the score.

Data errors or inconsistencies will be flagged and displayed immediately online during the data entry process. Data flags will either require ‘immediate correction’ or may be set as “warnings” (e.g., missing data). Immediate correction is required before the form is allowed to be submitted. The presence of warnings will not disallow submission of the form, but must be addressed in a timely manner. Errors that are warnings are entered into an error log and an error report will then be produced by the system. This report includes the error in the error log, its nature, the offending record ID, the data item ID, and the offending data value along with room to record the data correction. Any variables that are questioned as possibly being in error will be reported back to the Clinical Centers in a report called the Edit Report/Clarification Request. These reports will be site specific. This report will give the identification information for the variable in question (site number, patient code, form number, rating period), the variable name of the variable in question, the reason the variable is being questioned, the variable’s current value, and a space to correct the variable or indicate that the variable is correct as is. Sites will complete this report by accessing the TRTT website database and making the corrections or returning a report to the DCC verifying that the data as entered is correct.

Any new errors generated during editing are added to the error log. Errors that are corrected no longer appear in the error report but nevertheless remain in the error log to be used for monitoring, e.g. detecting error patterns. The process continues until there are no errors in the error report. Before the data may be used for interim or final analysis, all errors must be corrected or a decision to over-ride must be recorded. Unless authorized by study role, data corrections may only be applied to records and items flagged in the error log.

### **22.3.2 Data and Forms Tracking**

The TRTT forms tracking system updates the status of data collection forms as they proceed through all data processing steps. It will be used to generate monthly online reports of the status of all forms received that month and to assess enrollment milestones. Reports will be generated

from this tracking system and posted on the Clinical Center specific area of the TRTT website and also sent to the Clinical Center Coordinator on a monthly basis. Reports will monitor data collection forms expected from scheduled study visits, and will provide notification on the status of specific data collection forms (e.g., expected, completed, pending, missing). Updates can be completed if the key identifiers for a data collection form already exist in the database.

Reports generated on a monthly basis may include a:

- Missing Forms report that lists all expected forms that have not yet been entered;
- Outstanding Clarification Report that indicates the number of Edit Report/Clarification Requests that have not been received within 30 days of the date initiated;
- Expected Study Visits by participant visits; and
- Participant Status Report that lists all individuals whose eligibility remains pending.

This combination of reports will allow the Clinical Centers and DCC to monitor the quality of the data, as well as determine whether a Clinical Center is falling behind in the submission of data and corrections. The Project Coordinator will serve as a first-line resource for the Clinical Centers, working closely with them to help them understand the problems that the reports detect and correct the problems.

At the end of the study, the DCC will complete a final clean-up of the study database, working closely with Clinical Centers to ensure that all collected data have been entered into the database and that all entered data are as correct as can be made possible.

## **22.4 Quality Assurance**

For quality assurance, the following procedures will be monitored:

- Enrollment, including eligibility and randomization;
- Progression of Study Participants throughout the follow-up period;
- Data collection activities including completeness of data for each visit;
- Data capture during the data entry process;
- Visits scheduled within allowable time limits;

- Collection and submission of all expected data collection forms at study visits;
- Error trapping; and
- Error correction or data updates.

## **22.5 Confidentiality, Security, and Data Integrity**

To safeguard the confidentiality of Study Participants, at initial contact each participant will be assigned a unique, sequential Patient ID and a name code ID. Identifiers for potential participants from each Clinical Center will be generated before the study begins. As participants are screened, each ID number will be retrieved in sequence from the label sheet provided to each Clinical Center and assigned to potential Study Participants. The name code will be chosen by the Clinical Center. These IDs will be used to identify the study participant for the duration of the trial and must be entered to register the individual as a Study Participant. These identifiers must also be entered to access an online data collection form. To distinguish between identical data collection forms that are completed at different time points in the study (e.g., the Tinnitus Questionnaire), a date will be used as an additional ID field.

Security measures include password protection to block unwarranted intrusion into the database. In order to gain access to the system, the user must have a valid account and password and must be listed in the key staff list created at the time the study design and protocol are established. This list is accessible to the Database Programmer to allow for additions and deletions of an individual. When an individual has been deleted from the list, that person will no longer have access to study data even though he or she may have a valid account and password. If either component fails the lock and key check at entry, the user will receive a message to contact the database administrator by e-mail or telephone and will be blocked from entering the study database. In addition, to protect against unauthorized entry, each user will be granted privileges and views that allow access and limit function based purely on need. For instance, only those authorized users granted update authority will be permitted to change data.

Data integrity features include all procedures designed to protect the validity of the content and structure of data items, such as steps to protect against accidental errors at data entry, and update and policies and procedures designed to protect the structural integrity of the database system. Since relationships between tables (components) of a relational database are important, the database will be set up to enforce referential integrity that prevents breaking certain linkages e.g., deleting a record on which other records depend. In order to provide added protection, requests for record updates and deletions will be systematically implemented by the Database

Programmer. In addition to a restricted password, deletion control requires that the participant ID and form number be verified by duplicate entry before the deletion is executed. A record of the deletion will be maintained in the transaction log, and a copy of the deleted information will be retained in a deleted records log to allow for recovery of data if necessary.

All elements of the database will be backed-up daily and weekly onto high capacity cassette tapes and monthly backups will be transferred to CD media. In addition to those kept on site, copies of weekly backups will be stored off-site in a fireproof safe to permit retrieval of the data in the event of a total loss of information on site.

The database is a moving target, such that it is burdensome to attempt to reproduce snapshots of it at later points in time. “Frozen”, or official interim datasets, containing data entered “as of” a given date, will be created for monitoring purposes in conjunction with Data and Safety Monitoring Board interim monitoring report generation. These datasets will be archived for reference, and in order to duplicate analyses.

## **22.6 Data Sharing with Outside Investigators**

The TRTT data will become available to outside investigators at the conclusion of the trial and following publication of the main study findings (see Chapter 24). To facilitate sharing of data collected by the TRTT, an informational web-page will be added to the TRTT website by the DCC. The web-page will provide the following:

- Instructions for obtaining data;
- An application for data usage;
- A set of forms with an explanation of variable naming conventions;
- A data dictionary; and
- A data use agreement in PDF format.

The website will not be used for direct distribution of data but rather will be used only as a mechanism for informing researchers of the availability of the data, the potential for collaboration with the Center investigators, and the procedures for obtaining data for analysis.

Investigators requesting data for secondary analysis purposes will be asked to provide a proposal for the intended use of the data, and a list of the variables requested. All users will be

expected to enter into a data use agreement. Release of datasets to secondary users will be subject to approval of the TRTT Steering Committee.

To protect the confidentiality of participant data, only de-identified data will be made available for secondary analysis. Data records will be free of the personal identifiers specified in section 164.514(b)(2)(I) of the federal Privacy Rule. Indirect identifiers that would potentially compromise the anonymity of participants will be suppressed in all datasets released for public use. In addition, all secondary users of data will be asked to sign a data use agreement that stipulates conditions for use of the data. The agreement will specify the confidentiality and data security standards that must be adhered to by the recipient and will expressly stipulate that:

- The data are to be used for Institutional Review Board-approved research purposes only;
- No effort will be made to identify individual participants; and
- Data will not be transferred to other users by the recipient.

The data-sharing web-page will be advertised to potential users via the TRTT website and through newsletters targeted to the scientific community. A link to the data sharing web- page also will be maintained on the Johns Hopkins Bloomberg School of Public Health Center for Clinical Trial's website.

---

---

## Chapter 23

### **23.1 Introduction**

#### **23.1.1 Study Design**

The Tinnitus Retraining Therapy Trial (TRTT) is a multi-center randomized placebo-controlled trial designed to investigate the efficacy of Tinnitus Retraining Therapy (TRT) as a treatment for severe debilitating tinnitus of at least one year's duration. TRT is an habituation-based intervention that uses directive counseling (DC) and low-level sound therapy (ST) to facilitate habituation of the awareness of tinnitus, its annoyance, and impact on the patient's life. It will be compared with the standard of care (SC) as typically administered to patients with severely debilitating tinnitus in the military.

Within the trial, each Study Participant will be randomized to one of three treatment groups as shown in Table 23.1.

**Table 23.1 Schematic showing the three study groups**

	Sound therapy	“Counseling”
Group 1 (TRT)	Conventional Sound Generator	DC
Group 2 (partial TRT)	Placebo Sound Generator	DC
Group 3 (Standard of care)	Recommendation to use ambient sound	Standard clinical consultation as provided in the military

Randomization helps to ensure that treatment groups are balanced with respect to pretreatment characteristics, although analyses of departures from balance will be carried out with appropriate adjustment to treatment effect estimation, if needed. Randomization will be performed using permuted blocks of random size, and stratified by Clinical Center. The logistics of the randomization are described in Chapter 5, Patient Entry into the Study.

An important feature of this study is that every effort is made to keep the Study Audiologists and Study Participants blinded with respect to the type of sound generator (SG), either conventional or placebo.

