### 23.3.2 Statistical Analyses

The Data Coordinating Center will form a Coordinating Center Data Analysis Committee which will include the Data Coordinating Center Director, Study Biostatistician, and Statistical Programmer.

The Data Coordinating Center statistician will work closely with the DSMB and clinical investigators to arrive at appropriate statistical analyses, consistent interpretation of the data, and clear and unequivocal presentation of the TRTT findings to the medical community. Statistical analysis responsibilities include:

- Defining the outcome(s) to be evaluated in conjunction with clinical study investigators;
- Describing the differences between the treatment groups being compared with respect to the baseline variables which might contain prognostic information, and with outcome(s) of interest;
- Evaluating the strength of the evidence regarding differences between the treatment groups and making decisions on the basis of the evidence; and
- Recommending one of the treatment strategies or concluding that no recommendation can be made.

Initial analyses will be descriptive in nature, using means, standard deviations, and proportions to describe baseline characteristics of the sample for all participants combined and by intervention group. Distributions of continuous variables will be examined for symmetry, and transformations will be considered for seriously skewed variables. For continuous variables, one-way analyses of variance will be used to compare the intervention groups on demographic and other baseline characteristics; the purpose is to assess comparability among the randomly assigned groups. For dichotomous or other categorical variables, chi-square tests will be used to compare intervention groups, and enrolled/excluded groups. Pearson correlation coefficients will be calculated to assess the strength of the associations among the various outcome measures, and to examine associations of other covariates with outcome measures; such potential confounding variables will be considered for inclusion in secondary analyses involving regression models.

All primary analyses will be based on the “intention to treat” principle. Analyses will include the following:

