### 23.3.2.1 Primary Outcome

The primary outcome variable will be change in the TQ score. We will use spaghetti plots for initial exploratory analyses and longitudinal data analyses as our primary analytic method. Longitudinal analyses allows us to account for the natural correlation which occurs with observations on the same subject over time and for the same Audiologist observing several Study Participants. Indicator variables will identify group; their coefficients in the models represent the primary focus on group differences. Adjustment for covariates such as age and sex can easily be accounted for in this class of models.

Mean TQ scores will be compared between two treatment groups using Generalized Estimating Equations (GEE) as implemented in STATA, SAS or R. The basic model is as follows:

Let  $TQ$  denote the TQ score. We expect effects of Clinical Center, Audiologist, treatment group, and possibly personality traits as measured by the State-Trait Anxiety Index (STAI) or Positive and Negative Affect Schedule (PANAS); or other factors such as hearing difficulty measured using the Hearing Handicap Inventory (HHI), or early completion of treatment. We will use models of the form:

$$TQ_{ijkgt} = \beta_0 + \beta_c C_j + \beta_a A_k + \gamma_g G_g + \tau T_t + \rho_1 PT_{1i} + \rho_2 PT_{2i} + \varepsilon_{ijkgt}$$

where:

j indexes Clinical Center;  
k indexes Audiologist;  
g indexes Group;  
t indexes Time; and  
I indexes Study Participant.

Both Study Audiologist and Study Participant are nested within Clinical Centers. The parameter of interest is  $\gamma_g$ , with  $\gamma_1$  representing the difference between Group 1 (full TRT) and Group 3 (SC). (G represents a dummy variable for Groups).  $\beta_a$  and  $\beta_c$  provide comparisons between Study Audiologists and Clinical Centers; C and A are dummy variables.  $\tau$  captures the effect of time;  $T_1$  has the values of 0, 3, 6, 12, and 18.  $\rho_1$  and  $\rho_2$  capture differences in psychometric instruments measurements, e.g., the STAI and PANAS, respectively. Other factors may also be included as necessary ( $\rho_3$ ,  $\rho_4$ , etc.).

Similar models will be run for the secondary objectives. The mean TQ scores will be compared between the Group 1 (DC + conventional SG) and Group 2 (DC + placebo SG) for the superiority of the conventional SG; and between Group 2 (DC + placebo SG) and Group 3 (SC)

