### **23.3.2.2 Secondary Efficacy Analyses**

For the analyses looking at the difference between TQ score at baseline and 18 months, we will compare TQ mean scores at 18-month in the treatment phase among treatment groups using Analysis of Covariance (ANCOVA). We will adjust for Baseline TQ scores and heterogeneity of

tinnitus status in the patient population. We will also adjust for important baseline covariates and variables that may be unbalanced at baseline (even with randomization) and are potentially related to TQ score. We will also use GEE for this analysis.

The data resulting from this project will enable us to address a number of additional research questions. First, to assess the effect of the interventions on different aspects of tinnitus morbidity, we will use the approach described above with other outcome variables, including the TQ subscales, global and subscale scores of the Tinnitus Functional Index, the Tinnitus Handicap Inventory, and the visual analog scale of the TRT Interview instrument. We will also compare baseline audiometric measures, and psychoacoustic variables of Tinnitus Loudness Match and Loudness Discomfort Level to evaluate whether there is any change across time in these measures.

The secondary outcome variables are the same for both the primary objective and the secondary objectives. For both the objectives, all of the longitudinally assessed variables (for example, subscales of TQ, Tinnitus Handicap Inventory, Tinnitus Functional Index, TRT-Visual Analog Scale, Digit Symbol Substitution Task, tinnitus pitch and loudness match, and LDL) will be treated as the TQ score (primary efficacy outcome analysis) using GEE. The respective mean scores will be compared between corresponding treatment groups (as described in the previous section) over the entire treatment phase. Both the differences in mean responses between treatment groups and the rate of change over time will be of interest in these analyses.

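### Chapter 23 lets observed baseline imbalance and other open clauses decide which covariates adjust the treatment effect; one baseline-only set should be fixed before unblinding

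*Combined protocol and SAP*

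**What the plan says.** All of this is in Chapter 23.

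- **Section 23.1.1**, below Table 23.1, gives a general rule: "analyses of departures from balance will be carried out with appropriate adjustment to treatment effect estimation, if needed". It names no variables, no threshold and no analysis to which it is confined.
- **Section 23.3.2** plans baseline comparisons between the randomized groups. For continuous variables, "one-way analyses of variance will be used to compare the intervention groups on demographic and other baseline characteristics"; for categorical ones, "chi-square tests will be used to compare intervention groups". The stated purpose is to assess comparability. Covariates associated with outcomes are handled separately: "such potential confounding variables will be considered for inclusion in secondary analyses involving regression models".
- **Section 23.3.2.1** writes out the primary GEE with Clinical Center, Audiologist, group, time and two psychometric terms. The psychometric terms are introduced only as a possibility, early completion of treatment is listed among the factors that may matter, and the section ends: "Other factors may also be included as necessary". Time takes the values 0, 3, 6, 12 and 18, so baseline TQ is one of the outcomes and not a covariate.
- **Section 23.3.2.2** sets the 18-month ANCOVA. "We will adjust for Baseline TQ scores" is unconditional. Added to it are heterogeneity of tinnitus status and important baseline covariates, neither defined, and "variables that may be unbalanced at baseline (even with randomization) and are potentially related to TQ score".
- **Section 23.1.2** frames the primary hypothesis both as longitudinal TQ change and at the end of treatment. Section 23.2.3 claims power for either form.

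**The concern.** Under randomization, a baseline difference between arms is chance. Its size in this one trial is a poor guide to whether adjusting for the variable will sharpen the treatment estimate; that depends on how strongly the variable predicts TQ. A rule that responds to imbalance therefore tends to omit useful covariates in most trials and to admit them only when they happen to differ.

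The second issue is discretion. With no closed list, no threshold and no statement of which adjusted model is decisive, several defensible estimates will exist once the data are in. This reaches the primary claim in two ways: the ANCOVA serves the end-of-treatment part of the primary hypothesis, and the GEE has its own open clause.

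That clause also admits a variable that should not be there. Early completion of treatment occurs after randomization, and under Part 5 of the follow-up counseling script (Chapter 11, Appendix D) it is judged largely on whether tinnitus has improved. Adjusting for it would remove part of the effect being estimated.

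**Working it through.** **1. The plan's own sample size.** Inputs from Section 23.2.3: SD 12.5, difference 7, two-sided alpha 0.05 divided among three comparisons (equal split assumed: 0.0167, z = 2.394), power 80% (z = 0.842), attrition 10%.

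- n per group = 2 × (2.394 + 0.842)² × (12.5/7)² = 2 × 10.47 × 3.189 = 66.8, so 67. Then 67/0.9 = 74.4, so 75 per group and 225 in total.
- The t-test version gives 69 per group; 3 × 69 × 1.1 = 227.7. The stated 228 is reproduced.
- Evaluable per arm: 76 × 0.9 = 68.4, taken as 68. SE = 12.5 × √(2/68) = 2.144. At 7 points, 7/2.144 − 2.394 = 0.871, power 80.8% (79.9% by t). At 10 points, power is 98.8% (98.7% by t).

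These figures do not depend on the covariate question.

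**2. How often imbalance would change the model.** The plan gives no trigger. If it were p<0.05 on independent variables, at least one would be flagged by chance in 1 − 0.95^10 = 40% of trials with 10 variables, and 1 − 0.95^20 = 64% with 20.

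**3. What a fixed prognostic covariate gains.** Take 12.5 as the SD left after baseline TQ (an assumption), and let r be the further correlation of one covariate with the outcome. The residual SD is 12.5 × √(1 − r²), and the SE without the covariate is larger by 1/√(1 − r²).

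| r | SE with covariate | SE ratio without/with | Power at 7 points, fixed (t) |
|---|---|---|---|
| 0 | 2.144 | 1.000 | 79.9% |
| 0.1 | 2.133 | 1.005 | 80.3% |
| 0.2 | 2.100 | 1.021 | 81.7% |
| 0.3 | 2.045 | 1.048 | 83.9% |
| 0.5 | 1.857 | 1.155 | 90.9% |

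**4. What the imbalance-driven rule gains.** With a p<0.05 trigger, a useful covariate enters in only 5% of trials, so its benefit is almost never collected. Simulation (68 per arm, ten candidates, one prognostic) gives about 79% power at 7 points for r of 0.1 to 0.3, against 80 to 83% with the covariate fixed, and SEs 1 to 5% larger. These agree with the table within simulation error, about √(0.8 × 0.2/4,000) = 0.6 percentage points for 4,000 runs. At r = 0.5 the contrast is 80% against about 90%, with SEs 15% larger. With three prognostic covariates together explaining 10%, 30% or 50% of the variance, it is about 80% against 84%, 92% or 98%.

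At 10 points, power is 98 to 99% under every approach for r up to 0.3.

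**5. Type I error, nominal 1.67%.** Applied mechanically, the rule gave 1.1 to 1.4%. Reporting the better of the unadjusted and imbalance-adjusted results gave 1.7 to 1.9%, with simulation error about 0.14 percentage points. Only picking the best of three models, the third being a fixed prognostic model, reached 2.2 to 2.8%.

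**The case against.** A reader might infer more than the documents support, and four limits stand.

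- **Significance tests as the selector.** No section makes a p-value the trigger. Section 23.3.2 gives comparability as the purpose of the tests and states no cut-off. Linking them to the adjustment rule is a reasonable inference, not a stated method.
- **Any unbalanced variable gets in.** Section 23.3.2.2 also requires a potential relation to TQ, always keeps baseline TQ, and adds covariates judged important whether or not they differ. This is a loose prognostic set plus imbalance, not imbalance in place of prognosis.
- **The primary GEE is governed by imbalance.** The explicit clause sits under secondary efficacy analyses, and the correlation screen is confined to secondary models. The GEE's own open clause does not mention imbalance. However, the sentence in Section 23.1.1 has no such limit, and the end-of-treatment wording in Section 23.1.2 gives the ANCOVA a part in the primary hypothesis.
- **A ten-point power loss or a false-positive problem.** The 80% against 90% contrast needs a predictor with r = 0.5 left out of the model, while the obvious strong predictor, baseline TQ, is already in the ANCOVA. The 2.8% error rate needs a free choice among three models, one of which the plan does not contain.

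It can also be said that descriptive baseline tests harm no estimate by themselves. That is true as long as they do not choose covariates.

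**Conclusion.** The concern holds in a limited form. The plan lets observed imbalance help choose the adjustment, leaves both the GEE and the 18-month ANCOVA without a closed covariate set, and admits a post-randomization factor to the GEE. The main harm is that the decisive model can be chosen after the data are seen.

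The precision cost is small under moderate assumptions: about 79% against 80 to 83% power at 7 points, which concerns the component comparisons. It is negligible for the 10-point primary comparison. It would be larger only if a strong predictor were omitted. Mechanical use does not inflate type I error, and the trial's sample size is unaffected.

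The number of candidates, their prognostic strength, the p<0.05 trigger and the use of 12.5 as the SD after baseline TQ are assumptions; the documents give none of them. Only Part 2 of the document is shown, so a fixed covariate list in Part 1 cannot be excluded and would largely settle the point.

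**What to change.** Replace the conditional clause in Section 23.1.1, the imbalance clause in Section 23.3.2.2 and the open clause in Section 23.3.2.1 with one closed, baseline-only covariate set, fixed before unblinding and used in both the GEE and the 18-month ANCOVA:

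- baseline TQ and Clinical Center;
- named prognostic variables from those the plan already mentions, such as age, sex, STAI, PANAS and HHI. Specify their baseline values, because the last three instruments are repeated at 6 and 18 months (Sections 14.5.4 to 14.5.6).

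Remove early completion of treatment from the candidate factors. If baseline TQ becomes a GEE covariate, model only the 3, 6, 12 and 18 month scores as outcomes, since the current model also treats time 0 as an outcome. Describe baseline by arm, and state that the comparisons in Section 23.3.2 do not choose covariates. Label any imbalance-driven adjustment a sensitivity analysis.

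The cost is a change of SAP wording and a decision now on the named variables. What is given up is the freedom to react to a chance imbalance in the main estimate; the sensitivity analysis still shows whether it matters.
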